7.5.3 Quality of Life (QOL)

The Atrial Fibrillation Effect on Quality-of-Life (AFEQT™) includes 20 questions on a 7-point Likert scale. Questions 1-18 evaluate Health Related Quality of Life (HRQoL) and questions 19-20 relate to patients' satisfaction with treatment¹. The first 18 questions are used to calculate the Overall AFEQT score and the subscale scores across three domains as follows:

- AF related Symptoms: Four questions (1 – 4)
- Daily Activities: Eight questions (5 – 12)
- Treatment Concerns: Six questions (13 – 18)

The formula to calculate these scores is as follows:

$$100 - \left[\frac{(\text{sum of severity for all questions answered} - \text{number of questions answered}) \times 100}{\text{total number questions answered} \times 6} \right]$$

Overall and subscale scores range from 0 to 100. A score of 0 corresponds to complete disability, while a score of 100 corresponds to no disability.

Baseline AFEQT scores and changes from baseline at each timepoint the questionnaire is administered will be summarized descriptively for the following five scores. The overall AFEQT score and subscale scores across study visits will also be plotted.

- Overall AFEQT Score (18 questions)
- Symptom Subscale Score (4 questions)
- Daily Activities Subscale Score (8 questions)
- Treatment Concern Subscale Score (6 questions)
- Treatment Satisfaction Score (2 questions)

The AFEQT questionnaire will only be used in countries with validated languages. These analyses will be conducted for subjects in countries where the AFEQT questionnaires are applied.

7.6 Analysis of Additional Endpoints

Descriptive statistics will be provided on all additional endpoints in the analysis sets specified below.

7.6.1 Procedural data

Procedural data such as total procedure time, mapping time, PFA application time, number of PFA applications by PV and by subject, total fluoroscopy time, study catheter dwell time, ablation settings used, and use of paralytics and anesthesia will be summarized descriptively. These analyses will be conducted separately in the FAS and PP analysis sets.

7.6.2 Additional Safety Endpoints

The following analyses for the additional safety endpoints will be conducted in the mITT and FAS analysis sets and summarized descriptively as the total number of events, number of subjects with events, and percentage of subjects with events:

- Occurrence of individual PAEs from the primary composite
- Occurrence of Serious Adverse Device Effects (SADEs)
- Occurrence of Serious Adverse Events (SAEs) within 7 days (early-onset), 8-30 days (peri-procedural), and >30 days (late onset) of initial ablation procedure, separately for each timeframe
- Occurrence of non-SAEs
- Occurrence of clinically symptomatic severe PV stenosis as documented by computed tomography (CT)/ magnetic resonance angiogram (MRA)

7.6.3 Additional Effectiveness Endpoints

The following analyses for the additional effectiveness endpoints will be conducted separately in the FAS, mITT, and PP analysis sets and summarized descriptively:

- **Ablation by non-study catheter for PV isolation:** The number and percentage of subjects and number and percent of clinically relevant targeted PVs ablated by a non-study catheter (NSC) for PVI.

- Rate of ablation by NSC for PVI among all clinically relevant targeted pulmonary veins:

$$= \frac{\text{Number of PVs ablated by NSC}}{\text{Number of ablated PVs}}$$

- Rate of ablation by NSC for PVI among subjects:

$$= \frac{\text{Number of subjects with at least one PV ablated by NSC}}{\text{Total number of subjects ablated for PVI}}$$

- **Acute PV reconnection:** The number and percentage of subjects and number and percentage of targeted PVs where acute reconnection was identified by adenosine/isoproterenol challenge.

- Rate of acute PV reconnection among targeted veins:

$$= \frac{\text{Number of PVs with reconnection after adenosine/isoproterenol challenge}}{\text{Total number of PVs undergoing adenosine/isoproterenol challenge}}$$

- Rate of acute PV reconnection among subjects:

$$= \frac{\text{Number of subjects with PV reconnection in at least one PV after adenosine/isoproterenol challenge}}{\text{Total number of subjects undergoing adenosine/isoproterenol challenge in all PVs}}$$

- **Repeat ablation during the 12-month follow-up period**

- **Occurrence of repeat procedures:** Kaplan-Meier estimates and plots will be used to characterize the time to the first repeat ablation procedure for study related arrhythmia. The probability of freedom from repeat ablation for study related arrhythmia at each follow-up timepoint post index procedure will be presented. Additionally, the total number of repeat procedures, number of subjects undergoing a repeat procedure, and percentage of subjects undergoing a repeat procedure will be presented by type of arrhythmia treated (overall (all arrhythmias), AF and AFL or AT (left atrium)), and by timing of the repeat procedure (during the blanking period (Day 1-90) and during the evaluation period (Day 91-365)).

- **PV reconnection:** The number and percentage of subjects and number and percentage of targeted PVs at the repeat procedure where PV reconnection was observed

- Rate of PV reconnection among previously isolated veins:

$$= \frac{\text{Number of previously isolated PVs with reconnection identified at repeat}}{\text{Total number of previously isolated veins in subjects undergoing repeat ablation}}$$

- Rate of PV reconnection among subjects:

$$= \frac{\text{Number of subjects with PV reconnection identified at repeat procedure in at least 1 previously isolated vein}}{\text{Total number of subjects undergoing repeat ablation procedure with PVI in all targeted veins at index}}$$

- **Freedom from documented (symptomatic and asymptomatic) AF:** Kaplan-Meier estimates and plots will be used to characterize the time to first documented (symptomatic and asymptomatic) AF recurrence based on electrocardiographic data (≥ 30 seconds on arrhythmia monitoring device) during the effectiveness evaluation period (Day 91-Day 365). Acute procedural failure (i.e., failure to confirm entrance block in all PVs except those that are silent and/or cannot be cannulated post-procedure, use of non-study catheter for PV isolation, and failure to have PFA delivery with the study catheter due to IRE system malfunctions) will also be considered a failure. Subjects without effectiveness failure who undergo a repeat ablation procedure during the blanking period where PVs were ablated with a commercially available catheter and generator will be considered non-assessable for long-term effectiveness of the IRE ablation system and thus will be excluded from this analysis. The probability of freedom from documented (symptomatic and asymptomatic) AF at each follow-up timepoint post blanking will be presented.
- **Freedom from documented (symptomatic and asymptomatic) atrial arrhythmia (AF, AT or AFL):** Kaplan-Meier estimates and plots will be used to characterize the time to first documented (symptomatic and asymptomatic) AF/AT or AFL recurrence based on electrocardiographic data (≥ 30 seconds on arrhythmia monitoring device) during the effectiveness evaluation period (Day 91-Day 365). Subjects without effectiveness failure who undergo a repeat ablation procedure during the blanking period where PVs were ablated with a commercially available catheter and generator will be considered non-assessable for long-term effectiveness of the IRE ablation system and thus will be excluded from this analysis. The probability of freedom from documented (symptomatic and asymptomatic) AF/AT or AFL at each follow-up timepoint post blanking will be presented. The following criteria will also be deemed failures (see Appendix 1 of protocol for definitions):
 - Acute procedural failure (i.e., failure to confirm entrance block in all PVs except those that are silent and/or cannot be cannulated post-procedure, use of non-study catheter for PV isolation, and failure to have PFA delivery with the study catheter due to IRE system malfunctions)
 - Taking a new class I/III AAD for AF/AT or AFL for a previously failed class I/III AAD at a greater than the highest ineffective historical dose for AF/AT or AFL during the effectiveness evaluation period
 - Greater than 2 repeat ablations for AF/AT or AFL in the blanking period or any repeat ablation for AF/AT or AFL during the effectiveness evaluation period

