      - c) Right pulmonary veins position and ablate with contracted and wider loop
    - Use the maximum PFA level. Consider using the minimum PFA level when repeated applications are applied. Use clinical judgment and consider patient anatomy and the catheter position to determine if minimum PFA level should be used.
    - Do not allow ablation electrodes to overlap during application of PFA energy. Doing so may cause an error message to appear and stop the ablation before completion. In case of overlap, change the catheter position or turn off overlapping electrodes on the monitor to perform ablation.
  - All subjects will undergo PV ablation with the Circular IRE Catheter until PVI is achieved in all targeted PV'.
    - IRE ablation is to be used as the primary mode for PVI.

- If isolation is not obtained after circular PFA applications described above, review remaining signals and deliver PF energy with corresponding electrodes.
- ONLY after the investigator deems IRE ablation unable to achieve PVI should the lab be switched to commercial RF setup to complete the procedure (PVI only). Note, to prevent any risk to the patient, the IRE system should be completely disconnected prior to use of an RF system.
- Confirmation of entrance block (and exit block if SOC) (PVI) of all clinically relevant targeted PVs.
  - To verify entrance block, analyze electrograms in coronary sinus and/or atrial paced rhythm to confirm that no PV potentials are present.
- Ablation outside the PV region is NOT allowed with IRE ablation modality (further details below).
- Post PVI:
  - Administer adenosine/isoproterenol for each clinically relevant targeted PV to rule out dormant conduction
    - If any, treat reconnected PV regions by reviewing remaining signals on reconnection location and deliver PF energy with corresponding electrodes.
  - Confirmation and documentation of final entrance block (exit block is optional) (PVI) of all clinically relevant targeted PVs
    - To verify entrance, analyze electrograms in coronary sinus and/or atrial paced rhythm to confirm that no PV potentials are present.
    - Wave I: use Circular IRE Catheter AND Lasso® or PentaRay® for confirmation
    - Wave II: use Circular IRE Catheter, Lasso® or PentaRay® for confirmation per investigators choice
  - The ablation procedure is considered complete when confirmation of entrance in clinically relevant targeted PVs is confirmed.

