5 ANALYSIS SETS

For the analysis of study endpoints, the analysis sets defined in the following will be used:

- **Full Analysis Set (FAS):** The FAS analysis set will consist of all enrolled Wave I subjects who have had insertion of the study catheter (with or without delivery of pulse field ablation [PFA]).
- **Modified Intent-To-Treat (mITT) Analysis Set:** The mITT analysis set will consist of enrolled Wave I subjects who have had insertion of the study catheter and meet eligibility criteria.
- **Per Protocol Analysis Set (PP):** The PP analysis set will consist of Wave I subjects who satisfy the following criteria:
 - Have undergone ablation with the IRE ablation system.
 - Are treated for the study-related arrhythmia.
 - Are without major protocol deviations that would affect the scientific integrity of the primary safety and effectiveness data, including but not limited to the following:
 - Subjects found not meeting eligibility criteria
 - Use of the IRE ablation modality outside of the PV region
 - Failure to check for entrance block for each targeted PV after adenosine/isoproterenol challenge

Eligible subjects treated with commercially available catheters for non-PV triggers that may arise during the index procedure or during repeat procedures occurring during the blanking period will be followed for the full duration of follow-up and will be evaluable for all endpoints in order to preclude potential bias that would arise from exclusion of these subject profiles from endpoint estimates.

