7.4.2 Long-Term Effectiveness

The primary effectiveness endpoint is defined as freedom from documented (symptomatic and asymptomatic) atrial arrhythmia (atrial fibrillation [AF], atrial tachycardia [AT] or atrial flutter [AFL]) recurrence based on electrocardiographic data (≥ 30 seconds on arrhythmia monitoring device) during the effectiveness evaluation period (Day 91-Day 365). Acute procedural failure (i.e., failure to confirm entrance block in all PVs except those that are silent and/or cannot be cannulated post-procedure, use of a non-study catheter for PV isolation, or failure to have PFA delivery with the study catheter due to IRE system malfunctions) will also be considered a long-term effectiveness failure. Subjects without effectiveness failure who undergo a repeat ablation procedure during the blanking period where PVs were ablated with a commercially available catheter and generator will be considered non-assessable for long-term effectiveness of the IRE ablation system and thus will be excluded from this analysis.

The primary effectiveness endpoint will be summarized descriptively in the PP analysis set. The number and percentage of subjects free from primary effectiveness failure during the evaluation period will be presented.

The following additional analyses will be performed at the time of the effectiveness analysis:

- **Sensitivity to Analysis Set**

The primary effectiveness endpoint will be analyzed in the mITT and FAS analysis sets as sensitivity analyses.

- **Kaplan-Meier Analysis**

Kaplan-Meier estimates and plots will be used to characterize the time to the first primary effectiveness event, including acute procedural failure and documented symptomatic/asymptomatic AF, AT, or AFL recurrence following the initial ablation

procedure, in the FAS, mITT, and PP analysis sets. The probability of freedom from primary effectiveness failure at each follow-up timepoint post blanking will be presented.

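### The PV reconnection rates in SAP 7.6.3 pool veins isolated by PFA alone with veins that needed commercial RF, and no analysis set separates them

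*SAP*

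**What the plan says.** **Rates.** In the Wave I SAP, section 7.6.3, the vein-level acute reconnection rate is divided by "Total number of PVs undergoing adenosine/isoproterenol challenge". The vein-level rate at repeat ablation is divided by "Total number of previously isolated veins in subjects undergoing repeat ablation", and the subject-level rate at repeat by "Total number of subjects undergoing repeat ablation procedure with PVI in all targeted veins at index". None of these names the catheter or energy that achieved isolation. Wave II SAP 7.6.3 uses the same definitions with trivial wording differences.

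**Analysis sets.** The Wave I analyses "will be conducted separately in the FAS, mITT, and PP analysis sets and summarized descriptively"; Wave II uses mITT and PP. In both SAPs the PP set requires that subjects "Have undergone ablation with the IRE ablation system" but does not remove subjects in whom a non-study catheter was also needed for PVI. The PP sets in Protocol 20.3.1 and 20.3.2 do remove them.

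**Procedure.** Under Protocol 14.2.2.2, only after PFA is judged unable to isolate "should the lab be switched to commercial RF setup to complete the procedure (PVI only"). Entrance block is then confirmed. The step after PVI is: "Administer adenosine/isoproterenol for each clinically relevant targeted PV to rule out dormant conduction".

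**Related endpoints.** Acute procedural success (SAP 7.5.1) and primary effectiveness (SAP 7.4.2) both count use of a non-study catheter for PVI as failure. SAP 7.6.3 separately reports the share of veins and of subjects treated with such a catheter.

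**The concern.** Reconnection found at a repeat procedure is the study's vein-level evidence on whether PFA lesions last. Reconnection at the challenge is the matching acute evidence. A vein that PFA could not isolate, and that holds after RF, sits in both denominators as a vein that did not reconnect. If it reconnects, it is counted against PFA. Either way the rate describes the procedure as performed, not the PFA lesion. A reader who takes it as a measure of the study catheter would be misled by an unknown amount in an unknown direction.

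**Working it through.** The documents state no reconnection rate, vein count or RF share, so there is no plan figure to reproduce. The check has two parts.

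**1. Can an RF-completed vein enter each rate?**
- *Acute rate.* The switch to RF is described within the PVI step. The challenge follows and covers each clinically relevant targeted vein. A vein finished with RF during PVI is therefore challenged and counted.
- *Repeat rate.* A vein finished with RF at index is a previously isolated vein. If the subject returns for ablation, it is counted.
- *FAS and mITT.* Neither set has a catheter criterion.
- *PP.* A subject with PFA in three veins and RF completion in the fourth has undergone ablation with the IRE system, so all four veins stay. Under the protocol's PP definition the subject would have been removed.
- *Non-study-catheter rate.* It is reported beside the reconnection rates but not crossed with them.

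No listed set therefore yields a PFA-only rate in either wave.

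**2. How far could the pooled rate move?**
Let *s* be the share of counted veins that received RF, and *r*PFA and *r*RF the two reconnection rates.

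pooled = (1 − *s*) × *r*PFA + *s* × *r*RF

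shift = pooled − *r*PFA = *s* × (*r*RF − *r*PFA)

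All inputs below are assumptions.
- *General range.* With *s* = 2.5% and a 15-point difference, the shift is 0.025 × 15 = 0.4 points. With *s* = 20% and a 20-point difference, it is 0.20 × 20 = 4 points. The sign follows whichever energy reconnects more.
- *Repeat.* Take 6 subjects × 4 veins = 24 veins, 3 of them RF-completed, with 8 of the 21 PFA-only veins reconnected: 8/21 = 38.1%. The SAP rate is 8/24 = 33.3% if no RF vein reconnects, 10/24 = 41.7% if two do, and 11/24 = 45.8% if all three do.
- *Repeat, seen from the report.* A reported 6/20 = 30.0% with 3 RF-completed veins is compatible with a PFA-only rate of 6/17 = 35.3% (no RF vein reconnected) or 3/17 = 17.6% (all three did).
- *Acute, touch-ups only.* Take 38 subjects × 4 veins = 152 veins, 3 of them RF-completed before the challenge, with 15 of the 149 PFA-only veins reconnecting: 15/149 = 10.1%. The SAP rate is 15/152 = 9.9% if no RF vein reconnects and 18/152 = 11.8% if all three do.

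**The case against.** **What stands against the point.** These are descriptive additional endpoints, and in Wave I there are at most 40 subjects. In the repeat example the exact 95% interval for 8/21 is 18% to 62%, even ignoring clustering of veins within subjects, so a shift of a few points is small beside it. The all-vein acute denominator also follows the protocol summary, which defines acute reconnection over all clinically relevant targeted veins. Replacing it would depart from the protocol.

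Replacement could also do harm. Nothing confines RF to the time before the challenge. A vein isolated by PFA that reconnects and is then finished with RF is a true PFA reconnection, yet a filter to study-catheter-only veins would delete it. With 152 PFA-isolated veins, 15 reconnections and 3 of those later finished with RF, the right rate is 15/152 = 9.9%; the filter gives 12/149 = 8.1%, which flatters PFA. This objection decides the form of the fix.

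**Stronger readings the documents do not support.**
- A reader might infer that reported acute isolation itself is mixed. It is not: acute procedural success and primary effectiveness treat non-study-catheter use for PVI as failure.
- A reader might infer that SAP 7.4.2 applies the opposite principle, because it says some subjects "will be considered non-assessable for long-term effectiveness of the IRE ablation system". That rule concerns event-free subjects whose PVs are re-ablated commercially in the blanking period. For non-study-catheter use at index, the same paragraph keeps the subject and counts a failure.
- A reader might infer that subjects treated wholly with RF enter the rates. FAS and mITT can hold subjects with no PFA, but the SAPs do not say whether their veins are challenged or counted, and discontinued subjects are followed for only 3 months. The point rests on touch-up veins alone.
- A reader might say the RF veins are hidden. Their number is reported, so their effect can be bounded; what is missing is their reconnection status.

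**Conclusion.** The point holds in limited form. As defined, the reconnection rates in both SAPs combine PFA-only veins with veins that needed RF at index, and no analysis set isolates the former. They should not be read as reconnection of PFA lesions alone. Size and direction cannot be known from the documents. Under the assumed counts, the repeat rate moves from 4.8 points below to 7.7 points above the PFA-only value, and the acute rate from 0.2 below to 1.7 above. If RF completion proves rare, the effect will be negligible. Primary and secondary effectiveness conclusions and all hypothesis tests are untouched. The change is worth making because it is cheap and gives an interpretable rate for the study catheter.

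**What to change.** In section 7.6.3 of both SAPs, keep the all-vein rates and add vein-level and subject-level lines for two classes: veins treated with the study catheter only, and veins that received any non-study-catheter energy. At subject level, count a subject in a class if at least one vein belongs to it, and as reconnected if at least one such vein reconnected.

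- *Repeat ablation:* classify each vein by all energy delivered at the index procedure.
- *Acute reconnection:* classify by energy delivered before the adenosine/isoproterenol challenge, so that a PFA-isolated vein that reconnects and is then finished with RF still counts as a PFA reconnection.
- *If that timing is not recorded:* report the acute rate over all veins, with the number of non-study-catheter veins beside it.
- *Subjects with no PFA delivered:* state whether and how their veins enter these rates.

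Cost: SAP wording and two extra lines per rate. The per-vein non-study-catheter flag is already needed for another rate in 7.6.3. The item to confirm is the timing of RF relative to the challenge, which the non-exhaustive data list in Protocol 14.2.3.1 does not name. The split denominators will be small, above all at repeat ablation, and should be shown as counts with the percentages.

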7.6.4 Neurological Evaluations

The following analyses of neurological evaluations will be conducted using the mITT analysis set and summarized descriptively. In addition to the timepoints explicitly stated below, subjects will undergo full neurological follow-up only if neurologic symptoms and/or cerebral ischemic lesions are identified in a prior evaluation; results for these additional neurological evaluations will be summarized descriptively. Neurological evaluation questionnaires, including Mini Mental State Examination (MMSE), National Institute of Health Stroke Scale (NIHSS), and Modified Rankin Scale (mRS) will only be used in countries with validated languages. Only subjects in countries where the neurological evaluation questionnaires are applied will be included in the associated analyses.

- **Neurological Exam:** The occurrence of new or worsening neurological deficits post-ablation compared to pre-ablation will be summarized descriptively by timepoint.
- **Cerebral Emboli:** The frequency, anatomical location (side and area), and size (diameter and volume) of asymptomatic and symptomatic cerebral emboli observed pre-ablation and new emboli observed post-ablation as determined by Magnetic Resonance Imaging (MRI) evaluations assessed by a central core lab will be summarized descriptively by timepoint.
- **Mini Mental State Examination (MMSE):** The MMSE includes tests of registration, orientation (time and place), recall, attention and calculation, and language and praxis (naming, repetition, comprehension, reading, writing, and drawing)². The total score ranges from 0 to 30, with lower scores indicating greater cognitive impairment. MMSE scores pre-ablation and change from pre-ablation at the 1-month follow-up will be summarized descriptively. MMSE scores will also be plotted by timepoint.
- **National Institute of Health Stroke Scale (NIHSS):** The NIHSS is a 15-item quantitative measure of stroke-related neurologic deficit on the levels of consciousness, language, neglect, visual-field loss, extraocular movement, motor strength, ataxia, dysarthria, and sensory loss³. The total score ranges from 0 to 42, with scores equal to 0 indicating no stroke symptoms, score ranging 1-4 indicating minor stroke, ranging 5-15 a medium stroke, 16-20 a moderate to severe stroke, and a range 21-42 a severe stroke. NIHSS scores pre-ablation and post-ablation prior to discharge will be summarized descriptively and plotted by timepoint.
- **Modified Rankin Scale (mRS):** The mRS is a disability scale with possible scores ranging from 0 to 6, where 0 indicates no symptoms and 6 indicates subject expiration⁴. mRS scores pre-ablation and change from pre-ablation at the 1-month follow-up will be summarized descriptively. mRS scores will also be plotted by timepoint.

